4.10 Protocol Deviations

4.10.1 Major Protocol Deviation Criteria

Exact definitions of major protocol deviations affecting safety and efficacy analyses will be discussed at the blind review meeting and documented in the Blind Data Review and Analysis Sets Report. The Protocol Deviation and Non-Compliance Management Plan documents the process for identifying protocol deviations that would potentially exclude subjects from the PP Population.

If major protocol deviations occur as outlined in the criteria below, then the data from complete individual subjects, individual visits or individual evaluations will be excluded from the population of analysis as indicated.

Exclusion of subjects or observations from the analyses will be decided jointly by the CRO and Sponsor's Study Team prior to unblinding of the randomisation code and database release.

The subjects or observations to be excluded, and the reasons for their exclusion, will be documented and approved by the above-mentioned persons prior to database release. The documentation will be filed together with the remaining trial documentation.

The number of subjects in each analysis population will be reported. Major protocol deviations excluding subjects from any particular population will be described, reporting the number of protocol violators for each criterion. All major protocol deviations will be listed and summarised for all screened subjects.

Major protocol deviations will be classified according to the following categories:

- Concomitant Medication / Administration of Prohibited Medication;
- Inclusion or Exclusion Criteria;
- Informed Consent / ICF not signed or signed late;
- Informed Consent / Other;

CONFIDENTIAL

Sponsor:	Zambon S.p.A.	Protocol Number:	Z7224L01
----------	---------------	------------------	----------

- Investigational Product / Incorrect IMP kit given to subject;
- Investigational Product / IMP Dosing;
- Investigational Product / IMP Storage;
- Investigational Product / Other;
- Met Withdrawal Criteria but was not Withdrawn;
- Patient Privacy (PP) / PP not signed;
- Patient Privacy / Other;
- Randomization / Mis-stratification;
- Randomization / Multiple Randomizations;
- Randomization / Other;
- Randomization / Randomized Not Treated;
- Randomization / Treated and Not Randomized;
- SAE not reported or reported late;
- Study Procedure / Missed procedure;
- Study Procedure / Other;
- Study Procedure / Site Staff Authorization, Delegation, Training;
- Study Procedure / Subject compliance;
- Study Procedure / Unmasking (not per protocol);
- Study Procedure / Visit Missing;
- Study Procedure / Washout;
- Visit Window.

These categories may be amended or other categories may be added, but any changes will be made prior to database lock and will be documented in the Blind Data Review and Analysis Sets Report.

4.10.2 Protocol Deviations

Deviations from the protocol will be documented on an ongoing basis by the study monitors and clinical research associates or designee throughout the study period as detailed in the Protocol Deviation and Non-Compliance Management Plan.

At the time of database lock, prior to unblinding, the project manager or designee will forward all relevant documentation highlighting protocol deviations to the study statistician. These will be listed in the CTR. The study statistician will also verify occurrence of deviations from the protocol checking eCRF data, where feasible.

CONFIDENTIAL

Sponsor:	Zambon S.p.A.	Protocol Number:	Z7224L01
----------	---------------	------------------	----------

4.11 Missing Values – Missing Visits

The validity of the negative binomial model planned for the primary efficacy analysis of the mean annual NCFB exacerbation rate relies on the MAR assumption.

The validity of the log-rank test planned for the CCI and the supportive Cox proportional hazard regression model relies on the uninformative censoring assumption.

CCI analyses will be conducted to investigate the robustness of the conclusions of these analyses. A detailed description of these analyses is provided in Sections 4.7.4.2 and 4.7.6.1.

In the analysis of CCI total score and CCI domain scores, linear mixed models for repeated measures will be used to handle missing data. Under the MAR assumption, these models provide an unbiased estimate of the treatment effect that would have been observed if all subjects had continued on treatment [7].

The analysis of covariance model for the CCI will include only complete cases. CCI analyses might be added during the blind review meeting if the amount of missing data makes it reasonable for further investigations of their influence on the overall study results. Decisions will be documented in the Blind Data Review and Analysis Sets Report.

Unless stated otherwise, there will be no imputation of missing values and only observed data will be included in the summaries.

The number of subjects with missing data will be presented under a “Missing” category. Unless otherwise stated, missing values will be included in the denominator count when computing percentages.

When continuous data are being summarised, only the non-missing values will be evaluated for computing summary statistics.

In order to calculate the duration of last usage of colistimethate sodium/colistin and the time from last administration of colistimethate sodium/colistin, the following rules will be applied for partial dates of start and stop date of last administration of colistimethate sodium/colistin:

For the start date:

- if only the day is missing, the first day of the month will be assumed;
- if the day and the month are missing, then the date will not be imputed and the time/duration will be classified as “Not Evaluable”.

For the stop date:

- if only the day is missing, the last day of the month will be assumed;
- if the day and the month are missing, then the date will not be imputed and the time/duration will be classified as “Not Evaluable”.

Where a medication start date is partially or fully missing, and it is unclear as to whether the medication is prior or concomitant, it will be assumed that it is concomitant.

In case of a partial onset date of a NCFB pulmonary exacerbation due to missing day, the onset of the event will be assumed as the first day of the month. If the resultant derived date is prior to the date of first IMP dose, then it will be assumed to be equal to the first IMP dose date.

CONFIDENTIAL

Sponsor:	Zambon S.p.A.	Protocol Number:	Z7224L01
----------	---------------	------------------	----------

In case of a partial resolution date of a NCFB pulmonary exacerbation due to missing day, the resolution of the event will be assumed as the last day of the month. If the resultant derived date is after the treatment completion/discontinuation date, then it will be assumed to be equal to the treatment completion/discontinuation date.

In case a NCFB pulmonary exacerbation presents a symptom with missing duration, following a conservative approach, the longest duration will be imputed.

In order to calculate the duration of each course of systemic antibiotic therapy, the following rules will be applied for partial dates of start and stop date of systemic antibiotic therapies:

For the start date:

- if only the day is missing, the first day of the month will be assumed. If the resulting derived date is prior to the start date of the exacerbation, then start date of therapy will be assumed to be equal to the start date of the exacerbation.
- if the day and the month are missing, then the date will not be imputed.

For the stop date:

- if only the day is missing, the last day of the month will be assumed.
- if the day and the month are missing, then the date will not be imputed and the duration will be classified as "Not Evaluable".

The domain scores of the **CCI** will be considered non-missing if the following conditions are satisfied:

- Symptoms score: missing items ≤ 2 ;
- Activity score: missing items ≤ 4 ;
- Impacts score: missing items ≤ 6 .

If at least one domain score is missing, the total score will be considered as missing.

The domain scores of **CCI** will be considered non-missing if the responses are missing for half or less of the items in the domain.

If an AE has a partially or fully missing date, and it is unclear whether the AE is treatment-emergent, it will be assumed that it is. In the AEs analysis, when relationship to IMP is missing for a TEAE it will be imputed to be drug-related. Every effort should be made to query the site for complete data entry prior to database lock.

Other critical missing data, if any, will be discussed during the blind review of the data. Decisions will be fully documented in the Analysis Set Specifications Document.

4.12 Deviations from the SAP

Any deviations from the original SAP will be described and justified in the final CTR, whether written post interim or final analysis.

CONFIDENTIAL

Sponsor:	Zambon S.p.A.	Protocol Number:	Z7224L01
----------	---------------	------------------	----------

4.13 Changes in Conduct or Planned Analyses from the Protocol

Sections 2.2, 4.4.11, 4.7.5 and 4.7.6.3: The protocol incorrectly referred to the units for the determination of CCI [REDACTED] which have been reported as CCI [REDACTED] by the central laboratory.

Section 3.9: The rationale and results for a reassessment of the original sample size calculation are provided to explain the reduced target sample size and associated levels of power.

Section 4.7.4: The protocol states that the Negative Binomial Model will consider the log-time on study as offset. However, as specified in Section 4.1.7, NCFB Pulmonary Exacerbations analyses focus on the treatment period so log-time on treatment will be considered.

Section 4.7.6.1: The protocol states that CCI [REDACTED] = CCI [REDACTED]. For time-to-event endpoints, generally the + 1 is not included because this overestimates the time by 1 day for every event, therefore "+ 1" has been deleted.

Section 4.7.6.4: The protocol states that any episodes of pneumonia will be considered as severe pulmonary exacerbations. Any reported episodes of pneumonia which do not require intravenous antibiotics and/or hospitalisation will be data queried to amend the Preferred Term. However, any pulmonary exacerbation on the Pulmonary Exacerbation form of the eCRF that is linked to an adverse event with a Preferred Term of 'Pneumonia' but does not have any CCI [REDACTED] or CCI [REDACTED] will be assumed to be a severe NCFB pulmonary exacerbation.

Section 4.7.6.5: The protocol states that the CCI [REDACTED] total score will be computed and analysed. However, as recommended in the Manual Scoring Instructions CCI [REDACTED] only the CCI [REDACTED] domain scores will be presented and analysed.

There have been no other changes in analyses from those defined in the protocol.

CONFIDENTIAL

Sponsor:	Zambon S.p.A.	Protocol Number:	Z7224L01
----------	---------------	------------------	----------

4.14 Algorithms/SAS Codes

The SAS codes for descriptive statistics and frequency counts detailed below are examples only and other procedures may be used, if appropriate.

- **Tables that need descriptive statistics – continuous variables:**

```
PROC UNIVARIATE DATA=dset NOPRINT;
  VAR var1 var2 var3 ...varn;
  BY byvar; (optional)
  OUTPUT OUT= outset
  N=n MEAN=mean MIN=min MAX=max MEDIAN=median STD=std *Q1=q1
  Q3=q3; *Include Q1 and Q3 for CCI data only;
RUN;
```

- **Tables that need frequency counts:**

```
PROC FREQ DATA=dset NOPRINT;
  BY byvar; (optional)
  TABLES var1*var2 /out= outset;
RUN;
```

- **Tables that need T-Test;**

```
PROC TTEST DATA=dset;
  CLASS var1;
  VAR var1N;
RUN;
```

- **Tables that need exact 95% CIs for risk difference between groups for proportions and Fisher's Exact:**

```
PROC FREQ DATA=dset;
  BY byvar; (optional)
  TABLES var*treatment / MEASURES RISKDIFF EXACT ALPHA=0.05;
  EXACT MEASURES;
  OUTPUT OUT= outset EXACT MEASURES RISKDIFF;
  WHERE wherever; (optional)
RUN;
```

- **Tables that need 95% CIs within group for binomial proportions:**

```
PROC FREQ DATA=dset;
  BY byvar; (optional)
  TABLES var1;
  EXACT BINOMIAL;
  OUTPUT OUT= outset BINOMIAL;
RUN;
```

- **Tables that require analysis of (co)variance and 95% CIs between arms for continuous variables:**

```
PROC GLM DATA= dset OUTSTAT=outset;
  CLASS treatment psite med;
```

CONFIDENTIAL

Sponsor:	Zambon S.p.A.	Protocol Number:	Z7224L01
----------	---------------	------------------	----------

*MODEL change = treatment psite med baseline/ SOLUTION;
LSMEANS treatment / STDERR PDIFF CL OBSMARGINS;
BY byvar; (optional)
WHERE wherever; (optional)*

RUN;

Notes:

- Psite represents the pooled site, i.e. country, as detailed in [Section 4.9.1](#);
- Med represents use of stable concomitant therapy with oral macrolides (e.g. azithromycin or erythromycin or clarithromycin) (Yes/No);
- Change represents the change from baseline of the variable;
- Baseline represents the baseline value of the variable;
- Treatment order: 1= Colistimethate Sodium, 2= Placebo.

- **Tables that require Kaplan-Meier estimates and log-rank test:**

*PROC LIFETEST DATA=dset OUTSURV=LIFE METHOD=KM timelist=(0 28 90 180
270 EoT) reduceout;
TIME time*event (1);
ID subject;
STRATA treatment;
WHERE wherever; (optional)
RUN;*

Notes:

- Time represents the time to event or time to censoring;
- Event represents the censoring indicator (1 = censored);
- EoT should be replaced by the last time (in days) to event >270 days (if any);

- **Tables that require Cox proportional hazards model and 95% CIs of hazard ratios between treatments:**

*PROC PHREG data=dset;
CLASS treatment psite med;
MODEL time*event(1) = treatment psite med / ties=exact;
HAZARDRATIO 'Col. Sodium vs Placebo' treatment / cl=both;
BY byvar; (optional)
WHERE wherever; (optional)
RUN;*

Notes:

- Psite represents the pooled site, i.e. country, as detailed in [Section 4.9.1](#);
- Med represents use of stable concomitant therapy with oral macrolides (e.g. azithromycin or erythromycin or clarithromycin) (Yes/No);
- Time represents the time to event or time to censoring;
- Event represents the censoring indicator (1 = censored);
- If the option ties=exact requires a considerable amount of computer resources, the Efron approximation will be used (*ties=efron*).
- Treatment order: 1= Colistimethate Sodium, 2= Placebo.

CONFIDENTIAL

Sponsor:	Zambon S.p.A.	Protocol Number:	Z7224L01
----------	---------------	------------------	----------

- **Tables that require negative binomial modelling, including 95% CIs of treatment ratios:**

```
PROC GENMOD data = dset;
  CLASS treatment psite med;
  MODEL count = treatment psite med / offset=log_years link=log dist=negbin wald
  type3;
  ESTIMATE 'Col. Sodium / Placebo' treatment 1 -1 / exp;
  lsmeans treatment / ilink cl diff exp om;
  BY byvar; (optional)
  WHERE wherever; (optional)
RUN;
```

Notes:

- Psite represents the pooled site, i.e. country, as detailed in [Section 4.9.1](#);
- Med represents use of stable concomitant therapy with oral macrolides (e.g. azithromycin or erythromycin or clarithromycin) (Yes/No);
- Count represents the total number of exacerbations for each patient;
- log_years represents the logarithm of the follow-up time in years;
- Treatment order: 1= Colistimethate Sodium, 2= Placebo.

- **Tables that require linear mixed model for repeated measures and 95% CIs of differences between treatments:**

```
PROC MIXED data = dset;
  CLASS treatment visit psite med sub;
  MODEL change = treatment visit treatment*visit psite med baseline/ s ddfm=kr;
  REPEATED visit / subject=sub type=un r;
  LSMEANS treatment treatment*visit / om at means cl slice=visit;
  LSMESTIMATE treatment
  'Col. Sodium / Placebo' 1 -1 / cl;
  LSMESTIMATE treatment*visit
  'Col. Sodium / Placebo: Visit 4' 1 0 0 0 -1 0 0 0,
  'Col. Sodium / Placebo: Visit 5' 0 1 0 0 0 -1 0 0,
  'Col. Sodium / Placebo: Visit 6' 0 0 1 0 0 0 -1 0,
  'Col. Sodium / Placebo: Visit 7' 0 0 0 1 0 0 0 -1 / cl;
  BY byvar; (optional)
  WHERE wherever; (optional)
RUN;
```

Notes:

- Visit represents the clinic visit;
- Psite represents the pooled site, i.e. country, as detailed in [Section 4.9.1](#);
- Med represents use of stable concomitant therapy with oral macrolides (e.g. azithromycin or erythromycin or clarithromycin) (Yes/No);
- Sub represents the Subject Number;
- Change represents the change from baseline to each visit of the variable;
- Baseline represents the baseline value of the variable;
- Treatment order: 1= Colistimethate Sodium, 2= Placebo.

CONFIDENTIAL

Sponsor:	Zambon S.p.A.	Protocol Number:	Z7224L01
----------	---------------	------------------	----------

- **Tables that require Prentice, Williams and Peterson Total Time model and 95% CIs of hazard ratios between treatments:**

```
PROC PHREG data=dset;
  CLASS treatment psite med;
  MODEL (tstart , tstop)*status(1) = treatment psite med / ties=Breslow;
  STRATA episode;
  HAZARDRATIO 'Col. Sodium vs Placebo' treatment / cl=both;
  BY byvar; (optional)
  WHERE wherever; (optional)
RUN;
```

Notes:

- Psite represents the pooled site, i.e. country, as detailed in [Section 4.9.1](#);
- Med represents use of stable concomitant therapy with oral macrolides (e.g. azithromycin or erythromycin or clarithromycin) (Yes/No);
- Status represents the censoring indicator (1 = censored);
- Treatment order: 1= Colistimethate Sodium, 2= Placebo;
- Dataset for the analysis should be adequately created: Subjects with no events have a single observation, while subjects with one event have two rows etc... A pair of variables (tstart, tstop) is used to define the time interval of risk. The start time (tstart) is generally equal to 0 for the first event and equals to the last recurrence stop time for further events. During an episode of pulmonary exacerbation, the subjects can't have another episode. Therefore, they are by definition not at risk for a next event during a previous episode. The stop time (tstop) is a recurrent event time (status = 1) or a censored time (status = 0). The event order should be denoted by variable episode.

- **Multiple Imputation for pulmonary exacerbation rate**

An example of SAS code is provided below for the **CCI** analyses pulmonary exacerbation rate.

Missing at random and copy reference imputation

```
PROC GENMOD DATA=dataset1;
  MODEL count = treatment_d psite_d1-psite_dx med_d / OFFSET=log_years
  DIST=NEGBIN;
  /* >1000 imputations since some will be discarded due to convergence issues with the
  model */
  BAYES NBI=1000 NMC=11000 THIN=10 OUTPOST=dataset2 SEED=34783129;
RUN;

DATA dataset3;
  SET dataset2;
  RENAME treatment_d =c_treatment_d
  psite_d1-psite_dx=c_psite_d1-c_psite_dx
  med_d=c_med_d;
RUN;
```

CONFIDENTIAL

Sponsor:	Zambon S.p.A.	Protocol Number:	Z7224L01
----------	---------------	------------------	----------

```

PROC SQL;
  CREATE TABLE dataset4 AS
  SELECT dataset1.*, dataset3.*
  FROM dataset1, dataset3
  ORDER BY Iteration;
QUIT;

DATA dataset5;
  SET dataset4;
  BY Iteration;
  ARRAY c[*] c_psite_d1-c_psite_dx c_med_d;
  ARRAY x[*] psite_d1-psite_dx med_d;
  k=1/Dispersion;
  imp_subj=(years<365/365.25);
  years_imp=MAX(years,365/365.25);
  log_years_imp=LOG(years_imp);
  linpred_1=.;
  IF imp_subj THEN DO;
    years_miss=years_imp-years;
    linpred_1=Intercept;
    DO i=1 TO DIM(c);
      linpred_1+c[i]*x[i];
    END;
    linpred_mar=linpred_1+c_treatment_d*treatment_d;
    linpred_cr=linpred_1+c_treatment_d;
    y1hat_mar=years*EXP(linpred_mar);
    y2hat_mar=years_miss*EXP(linpred_mar);
    y1hat_cr=years*EXP(linpred_cr);
    y2hat_cr=years_miss*EXP(linpred_cr);
    CALL STREAMINIT(3231212);
    y2_mar=RAND('NEGBINOMIAL',(1+y1hat_mar)/(1+y1hat_mar+y2hat_mar),k+count);
    y2_cr=RAND('NEGBINOMIAL',(1+y1hat_cr)/(1+y1hat_cr+y2hat_cr),k+count);
    y_imp_mar=count+y2_mar;
    y_imp_cr=count+y2_cr;
  END;
  ELSE DO;
    y_imp_mar=count;
    y_imp_cr=count;
  END;
RUN;

```

Notes:

- dataset1 includes one record per patient;
- count represents the total number of exacerbations observed for each patient;
- treatment represents the treatment group (treatment order: 1 = colistimethate sodium, 2 = placebo);

CONFIDENTIAL

Sponsor:	Zambon S.p.A.	Protocol Number:	Z7224L01
----------	---------------	------------------	----------

- treatment_d represent the dummy variables for treatment group (values of the dummy variables: 0 for colistimethate sodium; 1 for placebo);
- Psite represents the pooled site, i.e. country, as detailed in [Section 4.9.1](#);
- psite d1-psite_dx represent the dummy variables for the (pooled) site;
- Med represents use of stable concomitant therapy with oral macrolides (e.g. azithromycin or erythromycin or clarithromycin) (Yes/No);
- med_d represents the dummy variable for use of stable concomitant therapy with oral macrolides;
- years represents the follow-up time in years;
- log_years represents the logarithm of the follow-up time in years.

Analysis step

The imputed dataset obtained using the above SAS code will be finally analysed and the results will be combined.

```
ODS OUTPUT LSMeans=lsmeans1 Estimates=ratios1;
PROC GENMOD DATA=dataset5;
  BY Iteration;
  CLASS treatment psite med;
  /* MAR imputation */
  MODEL y_imp_mar = treatment psite med / OFFSET=log_years_imp DIST=NEGBIN;
  /* Alternative MODEL statement: copy reference imputation */
  MODEL y_imp_cr = treatment psite med / OFFSET=log_years_imp DIST=NEGBIN;
  LSMEANS treatment / ilink cl diff exp om;
  ESTIMATE 'Col. Sodium / Placebo' treatment 1 -1 / exp;
RUN;
```

```
DATA lsmeans2;
  SET lsmeans1 (WHERE=(zValue ne .));
  BY Iteration;
  IF first.Iteration THEN _Imputation_+1;
  IF _Imputation_ LE 1000;
RUN;
```

```
ODS OUTPUT ParameterEstimates=lsmeans3;
PROC MIANALYZE PARMS=lsmeans2;
  CLASS treatment;
  MODELEFFECTS treatment;
RUN;
```

```
DATA lsmeans4;
  SET lsmeans3;
  exp_est=EXP(Estimate);
  exp_lcl=EXP(LCLMean);
  exp_ucl=EXP(UCLMean);
RUN;
```

CONFIDENTIAL

Sponsor:	Zambon S.p.A.	Protocol Number:	Z7224L01
----------	---------------	------------------	----------

```
DATA ratios2 (RENAME=LBetaEstimate=Estimate);
  SET ratios1 (WHERE=(ChiSq ne .));
  BY Iteration;
  IF first.Iteration THEN _Imputation_+1;
  IF _Imputation_ LE 1000;
  Effect='Label';
RUN;
```

```
ODS OUTPUT ParameterEstimates=ratios3;
PROC MIANALYZE PARMS =ratios2;
  CLASS Label;
  MODELEFFECTS Label;
RUN;
```

```
DATA ratios4;
  SET ratios3;
  exp_est=EXP(Estimate);
  exp_lcl= EXP (LCLMean);
  exp_ucl= EXP (UCLMean);
RUN;
```

- **Tables that require Non-Parametric Randomization-Based Analysis of Covariance.**

The macro NParCov4, reported in [Appendix 4](#), will be applied with the following parameters.

For the analysis of pulmonary exacerbation score:

```
%NPARCOV4 ( outcomes = outcome,
             covars = psite med,
             trtgrps = treatment,
             strata = NONE,

             hypoth = NULL /*for p-value*/,
             hypoth = ALT /*for CI*/,

             transform = NONE,

             dsnin = dataset,
             dsnout = outdat,
             exact = %str(NO)
           );
```

For the analysis of annualised number of pulmonary CCI:

```
%NPARCOV4 ( outcomes = outcome,
             covars = psite med,
             trtgrps = treatment,
             strata = NONE,
```

CONFIDENTIAL

Sponsor:	Zambon S.p.A.	Protocol Number:	Z7224L01
----------	---------------	------------------	----------

```
hypoth = NULL /*for p-value*/,  
hypoth = ALT /*for CI*/,  
  
transform = LOGRATIO,  
  
    dsnin = dataset,  
    dsnout = outdat,  
    exact = %str(NO)  
);
```

Notes:

- dataset includes one record per patient;
- outcome represents the outcome observed for each patient, ie the pulmonary exacerbation score or the annualised number of pulmonary CCI
- treatment represents the treatment group (treatment order: 1 = colistimethate sodium, 0 = placebo);
- Psite represents the pooled site, i.e. country, as detailed in [Section 4.9.1](#);
- Med represents use of stable concomitant therapy with oral macrolides (e.g. azithromycin or erythromycin or clarithromycin) (Yes/No);

CONFIDENTIAL

Sponsor:	Zambon S.p.A.	Protocol Number:	Z7224L01
----------	---------------	------------------	----------

5 Tables and Listings

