18.4.3. SAFETY DATA

All safety endpoints will be summarised and analysed using the Safety Population.

Incidence of Treatment Emergent Adverse Events

The number and the percentage of subjects reporting TEAEs, treatment emergent SAEs, severe TEAEs, TEAEs leading to discontinuation and TEAEs leading to death will be presented by treatment group, along with the number of events occurring.

TEAEs will also be summarised by System Organ Class and Preferred Term according to MedDRA; they will additionally be summarised by severity and relationship to treatment. A separate summary table will be provided for SAEs.

Only TEAEs, i.e. events with an onset date on or after the date of IMP start, will be included in the summary tables. Individual data listings will include all AEs recorded; a separate listing will be provided for treatment-emergent SAEs.

Number of Subjects experiencing Bronchospasm Clinically or Spirometrically Determined following IMP Administration

The number of subjects experiencing bronchospasm spirometrically determined (a >15% decrease in FEV₁ - not due to poor technique - from pre-bronchodilator baseline in the 30 minutes post-IMP), or clinically determined, will be summarised by treatment. Percentages of subjects in each treatment group and the relative risk for colistimethate sodium group/placebo group will be provided with 95% CI. Treatment differences will be assessed using a Fisher Exact test.

The number and the percentage of subjects experiencing a bronchospasm following IMP administration as clinically determined will also be reported by clinical visit.

In addition, the results for FEV₁ and FVC at each visit will be summarised by treatment. Descriptive statistics for absolute and percentage changes from baseline, i.e. Visit 2 (pre-dose measurement) will be reported.

CCI

The number and percentage of subjects whose CCI at the end of treatment (at 12 months [Visit 7]) will be presented by treatment, overall and by status of previous usage of colistimethate sodium/colistin.

Vital Signs

Descriptive statistics for vital signs at Visit 1 and Visit 7 will be presented overall and by treatment.

Physical examination data

Descriptive statistics for physical examination data at Visit 1 and Visit 7 will be presented overall and by treatment.

Haematology, clinical chemistry and renal function tests

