As a supportive analysis, the annualised number of [CCI] days will also be compared between the treatment groups using an ANCOVA model including treatment, pooled site, i.e. country, as detailed in Section 4.9.1, and use of stable concomitant therapy with oral macrolides as fixed effects. Least square means in each treatment group, least square mean difference between treatments, their 95% CIs and associated p-value will be estimated. OBSMARGINS option will be used for least square means estimates.

4.7.6.7 [CCI]

Total number of [CCI] and [CCI] will be described overall and by treatment group.

Total number of [CCI] per patient will be computed by summing [CCI] form. Number of [CCI] will be computed considering [CCI]. Namely:

- [CCI]

Where:

- $\frac{[CCI]}{[CCI]} = \text{sum} \{ [CCI] 1, [CCI] 2, \text{etc.} \} / [CCI]$
- $[CCI] \text{ Assessment } i = \text{Coeff } i * \{ (part1) [(Date of Assessment i) - (Date of Assessment i-1) + 1]/2 + (part2) [(Date of Assessment i+1) - (Date of Assessment i)]/2 \}$

Where Coeff i = 1 if Employment status equal to Employed or Temporarily Employed at Assessment i, Coeff i = 0 otherwise.

Treatment results will be compared using an independent groups t-test by means of the Satterthwaite method^[6]. The corresponding two-sided p-value will be presented. A two-sided p-value of <0.05 will be considered statistically significant. Mean difference, computed as colistimethate sodium - placebo, and corresponding 95% CI will also be presented.

The above summaries/analyses will be performed using the mITT Population.

Notes:

- [CCI] of first and last assessment will include only the subsequent period (referred to in the formula as part 2) and previous period (referred to in the formula as part 1), respectively.
- [CCI] relies on the assumption that no change [CCI] occurs during the [CCI] computed for each assessment.

4.7.6.8 [CCI]

The [CCI] will be provided overall and by treatment group. Percentages will be computed on the total number of subjects with at least one pulmonary exacerbation.

CONFIDENTIAL

Sponsor:	Zambon S.p.A.	Protocol Number:	Z7224L01
----------	---------------	------------------	----------

The relative risk of [CCI] for colistimethate sodium/placebo will be provided with 95% asymptotic CIs. Treatment differences will be assessed using a Fisher Exact test. A two-sided p-value of <0.05 will be considered statistically significant.

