4.8.2 Spirometry Results

The following spirometry parameters will be summarised for each visit, as applicable, by treatment group and overall:

- FEV₁ (L);
- Predicted FEV₁ (%);
- FVC (L);
- Predicted FVC (%);
- Change in FEV₁ (L) from pre-salbutamol/albuterol intake to 30 minutes post-IMP.

Absolute value and change from baseline at each visit will be described by means of summary statistics for continuous variables.

CONFIDENTIAL

Sponsor:	Zambon S.p.A.	Protocol Number:	Z7224L01
----------	---------------	------------------	----------

The number and percentages (along with exact 95% CIs) of subjects experiencing bronchospasm at Visit 7 (End of Treatment) following IMP administration as clinically (as collected in the Spirometry eCRF forms) or spirometrically (>15% decrease in FEV₁ from pre-salbutamol/albuterol intake to 30 minutes post-IMP) determined will be summarised by treatment. The number of subjects experiencing bronchospasm at all other visits will be listed. The subject will be considered spirometrically to have had a bronchospasm if presenting >15% decrease in FEV₁ from pre-salbutamol/albuterol intake to 30 minutes post-IMP or a positive answer to the above question.

The relative risk for colistimethate sodium/placebo will be provided with 95% asymptotic CIs. Treatment differences will be assessed using a Fisher Exact test. Subjects with no available result will be excluded from the analysis.

Notes:

- Change in FEV₁ (L) will be calculated as FEV₁ 30 minutes post-IMP – FEV₁ pre-salbutamol/albuterol intake;
- Percentage change in FEV₁ (%) will be calculated as 100*(change in FEV₁ [L] / FEV₁ pre-salbutamol/albuterol intake).

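### The example PROC FREQ code in SAP 4.14 crosses outcome by treatment, so if used as printed it does not return the colistimethate/placebo relative risk that the SAP text asks for

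*SAP*

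**What the plan says.** For bronchospasm at Visit 7, SAP 4.8.2 states: "The relative risk for colistimethate sodium/placebo will be provided with 95% asymptotic CIs". It adds: "Treatment differences will be assessed using a Fisher Exact test". Protocol 18.4.3 asks for the same ratio: "relative risk for colistimethate sodium group/placebo group will be provided with 95% CI".

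SAP 4.7.6.8 covers a secondary endpoint whose name is redacted. It asks for a relative risk "for colistimethate sodium/placebo will be provided with 95% asymptotic CIs", again with a Fisher exact test, and takes its percentages among subjects with at least one pulmonary exacerbation.

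SAP 4.14 gives the code. The only block for a two-group comparison of proportions is headed "Tables that need exact 95% CIs for risk difference between groups for proportions and Fisher's Exact", and its table request is "TABLES var*treatment / MEASURES RISKDIFF EXACT ALPHA=0.05". The note "Treatment order: 1= Colistimethate Sodium, 2= Placebo" is printed under several model blocks in the same section, though not under this one. The section opens by saying that code for descriptive statistics and frequency counts consists of items that "are examples only and other procedures may be used, if appropriate".

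**The concern.** In a two-way PROC FREQ request the variable before the asterisk forms the rows and the one after it the columns. For a 2x2 table, row risks, the risk difference and the relative risk are all computed within rows. The placeholder `var` is not defined, but with treatment as the other factor it can only sensibly be the binary outcome. The printed request then conditions on the outcome and reports the proportion of subjects who were on colistimethate. The heading promises a comparison between groups, whereas the statistic returned compares outcome levels.

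At stake are the effect estimate and interval for a named safety endpoint (bronchospasm after dosing, Table 14.3.4.1.2) and for one secondary endpoint. Fisher's p-value does not change when a 2x2 table is transposed, so checking the p-value would not expose the slip.

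**Working it through.** The plan gives no figure to reproduce here. The check applies the 2x2 definitions to both layouts. All event counts below are assumptions, because the documents contain none.

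**Formulas.** With cell counts n11, n12 in row 1 and n21, n22 in row 2:
- row risk = n_i1 / (n_i1 + n_i2)
- relative risk (column 1) = row 1 risk / row 2 risk
- standard error of log RR = sqrt[(1 − r1)/n11 + (1 − r2)/n21]
- 95% CI = RR × exp(±1.96 × SE)

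**Illustration A: the 4.7.6.8 denominator** (subjects with at least one exacerbation). Assume 20 events in 90 on colistimethate and 30 in 105 on placebo.

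Intended layout, `treatment*var` with the event in column 1:
- risks 20/90 = 0.222 and 30/105 = 0.286; RR = 0.78
- SE = sqrt(0.778/20 + 0.714/30) = 0.250; 95% CI 0.48 to 1.27

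Printed layout, `var*treatment` with colistimethate as column 1:
- event row 20/(20 + 30) = 0.400; no-event row 70/(70 + 75) = 0.483
- event row first: RR = 0.400/0.483 = 0.83; SE = sqrt(0.600/20 + 0.517/70) = 0.193; 95% CI 0.57 to 1.21
- no-event row first: RR = 0.483/0.400 = 1.21; 95% CI 0.83 to 1.76

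Reading the placebo column does not help: (30/50)/(75/145) = 1.16, or 0.86 with the rows reversed. None of the four values is 0.78. Fisher's p is 0.33 in every layout.

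**Illustration B: an interval that misleads.** Assume 19 versus 9 events with 188 per arm. These are full-arm numbers for arithmetic only; 4.8.2 excludes subjects with no available result, so the bronchospasm denominators would be smaller.

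| Layout | Row risks | RR (95% CI) | Fisher p |
|---|---|---|---|
| `treatment*var`, event in column 1 | 19/188 = 10.1%, 9/188 = 4.8% | 2.11 (0.98 to 4.55) | 0.075 |
| `var*treatment`, event row first | 19/28 = 67.9%, 169/348 = 48.6% | 1.40 (1.06 to 1.84) | 0.075 |
| `var*treatment`, no-event row first | 48.6%, 67.9% | 0.72 (0.54 to 0.94) | 0.075 |

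In the last two rows the interval excludes 1 beside a Fisher p of 0.075. In the last row a doubling of risk reads as a reduction.

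**Equal risks.** With 10 events in each arm of 188, both layouts give RR 1.00, but the intervals still differ: 0.43 to 2.35 intended, 0.64 to 1.57 printed.

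**The case against.** The strongest defence is that the specification lies in the prose, and the prose is right. Sections 4.8.2 and 4.7.6.8 both define the ratio as colistimethate over placebo, and the code is a template with undefined placeholders in a section that allows other procedures. Much of this stands: the fault is in the example code and not in the planned estimand. It is not a complete answer. The disclaimer names descriptive-statistics and frequency-count code, each of which has its own block, so it does not clearly cover this inferential one. Even if it does, no other two-group proportion code is printed.

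The block is headed for a risk difference and Fisher's test, so its use for these relative risks is an inference. That is fair, though the MEASURES option would print a relative risk. It is also true that no SAP section asks for a between-arm risk difference, so a distorted one would have no planned table to appear in.

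A programmer or reviewer could catch the mismatch. Both sections call for results by treatment group, and arm percentages of 10.1% and 4.8% beside a relative risk of 1.40 or 0.72 would look inconsistent. The SAP Addendum (section 9) describes quality control of program logic and output. These safeguards reduce the chance of a wrong table but do not correct the printed line.

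A reader might infer that the reported relative risks are wrong, or that the direction is certainly reversed. The documents support neither. They do not show which code the final programs used, and reversal depends on the coding and sort order of `var`, which the SAP does not state.

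**Conclusion.** The point holds as a conditional error in the example code. If the SAP 4.14 line is used as printed for bronchospasm or the 4.7.6.8 endpoint, the relative risk and its asymptotic interval do not estimate the quantity the SAP text defines, and the direction reverses if the no-event level sorts first. In the assumed 20/90 versus 30/105 example, 0.78 becomes 0.83 or 1.21.

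This rests on reading `var` as the binary outcome and on colistimethate being column 1, as the treatment-order notes elsewhere in 4.14 indicate. The counts are illustrative.

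Fisher's p-value, the only test named for either endpoint, is unchanged, so any decision taken on it within the secondary hierarchy is unchanged too. The primary negative binomial analysis is not involved. Severity is minor to moderate, limited to effect estimates and their intervals.

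**What to change.** Replace the request with `TABLES treatment*var / RELRISK`, and ask for Fisher's test through the FISHER or EXACT option. Order treatment as colistimethate then placebo, and select the event column explicitly so that the result does not depend on how the outcome is coded or sorted. Drop RISKDIFF, or keep it only if a between-arm risk difference is to be reported. Reword the block heading to name the relative risk with asymptotic limits.

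Check the programs behind Table 14.3.4.1.2 and the 4.7.6.8 table. Rerun only if they used the printed layout, and record the outcome of the check either way. The cost is one line of code and a short program review. Should a rerun be needed, there is a precedent: the note to file on grouped countries already provides for rerunning two tables to correct a double-counting issue.
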